4.1 Phase I Dose Limiting Toxicities

- 1) Grade 4 non-hematologic toxicity (not laboratory).
- 2) Grade 4 hematologic toxicity including Grade 4 neutrophil count decrease, Grade 4 platelet count decrease or Grade 4 anemia regardless of duration.
- 3) Grade 3 Neutrophil count decrease lasting > 1 week, or febrile neutropenia.
- 4) Grade 3 Platelet count decrease lasting > 1 week, or Grade 3+ thrombocytopenia with bleeding.
- 5) Grade 3 non-hematologic toxicity (not laboratory) will be considered a DLT with the following exceptions: grade 3 fatigue, Grade 3 nausea, vomiting, or diarrhea lasting < 72 hours, (Grade 3 nausea, vomiting, or diarrhea lasting >72 hours despite optimal supportive care is a DLT).
- 6) Any Grade 3 non-hematologic laboratory value if:
 - Associated with clinical symptoms or signs, or
 - Medical intervention is required to treat the patient, or
 - The abnormality leads to hospitalization, or
 - The abnormality persists for >1 week.
- 7) AST and/or ALT elevation >20 x ULN with concurrent total bilirubin elevation to >5 x ULN

without initial evidence of cholestasis.

8) Grade 5 toxicity (i.e., death).

The treatment related toxicities should be evaluated as CD24Fc treatment emergent AE that is not associated to irAEs defined in enrollment. The DLT monitoring period is the 14 days after the first dose of CD24Fc at 480 mg. If DLT occurred in 2 patients during the first dose of CD24Fc dosing in the 14-day period, CD24Fc will be reduced to 240 mg as first dose, or 120 mg until no more than 1/6 patients developed DLT. The study will be terminated if >2 patients have DLT at this reduced dosing. In Phase I, patients will be dosed at least two hours apart and no more than two patients will be enrolled in the same day.

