6.4.3 Dose adjustment

There should be a one level dose reduction (i.e., CD24Fc 240 mg on day 1, 120 mg on day 14, and 120 mg on day 28 i.v.) if any \geq G3 hematologic due to CD24Fc that requires < 2 week to recover to grade 1 or less. There will be no dose reduction according to irAEs.

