6.7 Criteria for Removal from Protocol Treatment

- Unacceptable toxicity (as determined by the treating physician and/or the patient), or toxicity requiring discontinuation of treatment (See sections 4.0 and 4.1).
- Elevation in AST or ALT $>20x$ ULN on bloodwork prior to CD24Fc treatment.
- Elevation of total bilirubin $>5x$ ULN on bloodwork prior to CD24Fc treatment.
- If the recovery of any $\geq G3$ hematologic or non-hematological toxicity due to CD24Fc to grade 1 or less requires > 2 weeks.
- Patients may choose to withdraw from the study at any time for any reason.
- Patients may be withdrawn from the protocol at the investigator's discretion if the investigator feels that continuation is not in the patient's best medical interest or if the patient is non-compliant with treatment.
- Completion of treatment CD24Fc.
- All reasons for discontinuation of treatment must be documented in the case report forms.
- Therapy after Protocol Treatment is stopped: If patients fail to respond to the protocol treatment and/or are removed from the therapy because of toxic effects or "disease progression", further treatment, if any, is at the discretion of the investigator.

Follow-up off Protocol Treatment: After removal from protocol treatment, all patients will be followed for late toxicities. Patients will be seen 4 weeks, 4 months and 7 months after coming off therapy. If ongoing toxicities have not resolved to \leq grade 1 within the first 4 weeks, patients are to be seen every month until toxicity resolves to \leq grade 1. No new toxicities after the 4-week follow-up will be re-reported unless considered related to protocol treatment by the investigator.

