10.2 Statistical Analysis

Demographic and background characteristics obtained at enrollment will be listed and summarized. Descriptive statistics will be used to summarize changes of biomarkers from baseline in clinical laboratory parameters for this cohort, and use of steroids (drug, dose, duration) and other treatment for irAE. We will adjust steroids use in analyses. Subgroup analyses will be performed separately by the status of Steroids use.

To assess toxicity: Toxicity is evaluated by NCI CTCAEv5.0. The type, grade, frequency and proportion of toxicities noted during the treatment period will be reported, along with associated 95% confidence interval of proportion. All adverse events noted by the investigator will be tabulated according to the affected body system. In phase I lead-in study, dose limiting toxicity is defined as any new AE of \geq grade 3 that are outside the spectrum of irAEs.

To assess time to recovery from irAE (time to reduction of irAE by at least one grade), time to all irAEs reduced to ≤ 1 , and time to resume ICI treatment: All time points will be started from Day 1 of CD24Fc treatment. Kaplan-Meier plots and confidence intervals will be used to summarize outcomes. Medians and associated 95% confidence intervals will be calculated, and comparisons between groups will be

performed by log-rank tests. Cox proportional hazard models will be used to explore association between covariates and outcomes.

To assess recovery rate of CD24Fc (reduction of irAE by at least one grade) at D42 and response rate of ICI: The fraction of patients who experience a PR or CR will be determined by dividing the number of responders by the total evaluable patients. The fraction will be reported along with 95% two-sided confidence intervals. Comparisons between groups will be performed by Fisher's Exact tests. We will also characterize the proportion who remain that either respond or have stable disease, compared to those who progress.

To assess PFS and OS: Kaplan-Meier plots and confidence intervals will be used to summarize PFS, and OS; 1-year OS rate will be reported; medians and associated 95% confidence intervals will be calculated, and comparisons between groups will be performed by log-rank tests. Cox PH models will be used to explore association between outcomes and covariates.

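### Scheduled Phase I blood draws cannot show the one-week duration that three DLT criteria require within the 14-day window, and the plan carries two conflicting DLT definitions

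*Combined protocol and SAP*

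**What the plan says.** Section 4.1 lists eight kinds of Phase I DLT. Three include a duration criterion for a Grade 3 laboratory change:

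- item 3: "Grade 3 Neutrophil count decrease lasting > 1 week, or febrile neutropenia";
- item 4: "Grade 3 Platelet count decrease lasting > 1 week, or Grade 3+ thrombocytopenia with bleeding";
- item 6, other laboratory values, where one of four alternatives is "The abnormality persists for >1 week".

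The same section sets the window: "The DLT monitoring period is the 14 days after the first dose of CD24Fc at 480 mg". The dose-reduction trigger follows: "If DLT occurred in 2 patients during the first dose of CD24Fc dosing in the 14-day period", the starting dose comes down.

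Table 1 schedules CBC and CMP at screening, Day 1, Day 14 ± 3, Day 28 ± 3 and later visits. Footnote 5 lets each dosing-day draw be taken up to 3 days before the infusion.

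The synopsis (Statistical Considerations) and Section 10.2 define a DLT in one line: "In phase I lead-in study, dose limiting toxicity is defined as any new AE of" grade 3 or higher that falls outside the irAE spectrum. That line has no duration criterion and none of the exceptions listed in 4.1.

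**The concern.** A criterion that needs more than a week of observation sits in a two-week window with at most one scheduled draw after dosing. Section 4.1 does not require a repeat draw. It does not say whether an event that begins in the window but is confirmed later counts, or what happens if persistence is never measured.

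Phase I has 6 patients and the trigger is 2, so the classification of one patient can decide whether the dose is reduced. Take a new Grade 3 neutrophil value at the Day 14 draw, outside the irAE spectrum and without fever. Under the synopsis and 10.2 it is a DLT at once. Under 4.1 it is open until persistence is shown, and it may stay open. The same data can give different DLT counts.

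**Working it through.** The plan gives no figure for how soon persistence can be confirmed, so there is none to reproduce. The check lists the draw days that the schedule allows.

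**Inputs.** Dose 2 on Day 11-17 and dose 3 on Day 25-31 (Table 1); each draw 0-3 days before the dose (footnote 5); window of 14 days after Day 1, so it ends on Day 1 + 14 = Day 15 (Day 14 if Day 1 is counted); duration of more than 7 days (4.1).

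**1. Draws inside the window.** The first draw after dosing falls between Day 11 − 3 = Day 8 and Day 17 − 0 = Day 17. Those inside the window are Day 8-15, which is 8 possible days. A draw on Day 16 or 17 leaves no scheduled value in the window at all.

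**2. Can more than 7 days be shown by Day 15?** For a first Grade 3 value on day d, the earliest day that is more than 7 days later is d + 8.

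- d = 8 gives Day 16, 1 day late.
- d = 15 gives Day 23, 8 days late.

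So 0 of 8 days work. If the window ends on Day 14, 0 of 7 work. An extra redraw while a dose is rescheduled (6.3, 6.4.0) does not help: the widest in-window span is 15 − 8 = 7 days, which is not more than 7.

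**3. The next scheduled draw.** It falls between Day 25 − 3 = Day 22 and Day 31. The gap from an in-window draw is 22 − 15 = 7 to 31 − 8 = 23 days, nominally 28 − 14 = 14. A value still Grade 3 after a gap of more than 7 days supports persistence. A value that has recovered lasted, on the nominal schedule, anywhere from 0 to 14 days after it was first seen, so the criterion stays undecided.

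**4. Patients taken off treatment.** Section 4.0 stops drug for a Grade 3 or higher toxicity at least possibly related to CD24Fc. The first off-therapy visit in 6.7 is 4 weeks later: Day 36-43 counted from the draw (8 + 28 to 15 + 28), or Day 39-45 counted from the visit (11 + 28 to 17 + 28). Section 6.7 names no laboratory test for that visit.

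Two other rules suggest that some cases continue on treatment. Section 6.4.3 reduces the dose for a Grade 3 or higher toxicity described as "hematologic due to CD24Fc that requires < 2 week to recover to grade 1 or less". Section 6.7 removes the patient if recovery of a "toxicity due to CD24Fc to grade 1 or less requires > 2 weeks". Both depend on recovery time and neither sets a draw to measure it.

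**5. One new in-window Grade 3 neutrophil value, no fever, outside the irAE spectrum:**

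| Rule applied | Status |
|---|---|
| Synopsis and 10.2 | DLT at once |
| 4.1, counted by onset | Open until persistence is shown; possibly never settled |
| 4.1, counted by completion | Not a DLT on scheduled draws |

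**6. Why no exposure figure is claimed.** The synopsis expects 4-5 enrolments a month, but it also allots 3 months to Phase I, which can be read as 6 / 3 = 2 a month. Assume even spacing s and that the first two patients are affected. The second patient's status at the off-therapy visit is then known s + 35 to s + 44 days after the first patient's first dose.

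- At 4-5 a month, s = 30.4/5 = 6.1 to 30.4/4 = 7.6 days. Status is known at 41-52 days. The sixth patient is dosed at 5s = 30-38 days, so all 6 have been dosed.
- At 2 a month, s = 15.2 days. Status is known at 50-59 days. The fourth patient is dosed at 3s = 46 days and the fifth at 4s = 61 days, so 4 have been dosed.

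**The case against.** **Section 4.1 evidently governs.** The trigger sits directly under the eight-item list, and the removal rules in 4.0 and 6.7 point to 4.1. A reader might infer that nothing in the plan indicates which definition drives the trigger; that goes too far. What remains is that the statistical section states a different definition without referring to 4.1.

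**Onset is the natural reading.** Even with daily draws, an event starting on Day 8 or later cannot pass 7 days by Day 15. A reader might infer that a persistent value first seen at the Day 14 draw can never count. That needs the strained completion reading, which the text does not require. Counting by onset still leaves open how and when persistence is confirmed.

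**Clinicians will recheck.** The recovery-time rules presuppose follow-up values, Section 13.1 calls for ongoing safety review, and Table 1 does not bar unscheduled draws. This is fair, and it makes long delays less likely. But none of these texts names a draw or a time, and 13.1's bi-weekly monitoring names no laboratory test.

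**Consequences are limited.** Drug already stops for a related Grade 3 toxicity. The Grade 4, fever, bleeding, symptom, intervention and hospitalization criteria need no one-week duration. The report on continuing (6.6) follows the sixth patient's third dose. All of this stands, although no rule says that later data count toward the 14-day tally.

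**Exposure.** A reader might infer that all six patients would be dosed before the trigger could act. That depends on the accrual rate, as step 6 shows. Section 4.1 also allows two enrolments on one day and sets no pause for DLT status, so laboratory timing would not be the only cause.

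**Conclusion.** The point holds in a limited form. Scheduled draws cannot establish the one-week criteria of items 3, 4 and 6 inside the window (0 of 8 draw days; 0 of 7 if it ends on Day 14), and some values may never be classifiable. The one-line definition in the synopsis and 10.2 conflicts with 4.1, although 4.1 is the likelier governing text.

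This rests on scheduled draws only and on the visit windows in Table 1 with footnote 5. The documents give no rate of Grade 3 laboratory events and leave accrual open at about 2 to 5 a month. They therefore support neither a probability of a missed trigger nor a number of patients exposed. Priority is minor to moderate: more than missing detail, because a two-in-six rule can be counted in different ways, but confined to the one-week criteria.

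**What to change.** 1. In the synopsis and Section 10.2, replace the one-line definition with *DLT as defined in Section 4.1*. Keep the new grade 3 or higher event outside the irAE spectrum as the Phase I primary endpoint.
2. State in 4.1 that a Grade 3 laboratory value first recorded in the 14-day window counts toward the trigger if it lasts more than 7 days, even when this is shown after the window.
3. State that such a value counts as a DLT unless a repeat CBC/CMP within 7 days of the first Grade 3 value shows recovery below Grade 3. Apply this also to patients taken off treatment.

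A repeat within 7 days is the useful interval: recovery seen by then shows that the value did not last more than 7 days from its first record. A single later repeat would leave a recovered value undecided. With first values on Day 8-15, the repeat is due by Day 15-22, so status closes at most 22 − 15 = 7 days after the window.

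The cost is an occasional routine blood draw, later closure of DLT status for affected patients, and a conservative count when no repeat is taken. Onset before the first recorded value is still not dated, and a first draw on Day 16 or 17 still falls outside the window.

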	
Demographic and background characteristics obtained at enrollment will be listed and summarized. Descriptive statistics will be used to summarize changes of biomarkers from baseline in clinical laboratory parameters for this cohort, and use of steroids (drug, dose, duration) and other treatment for irAE.
 
To assess toxicity: Toxicity is evaluated by NCI CTCAEv5.0. The type, grade, frequency and proportion of toxicities noted during the treatment period will be reported, along with associated 95% confidence interval of proportion. All adverse events noted by the investigator will be tabulated according to the affected body system. In phase I lead-in study, dose limiting toxicity is defined as any new AE of \geqgrade 3 that are outside the spectrum of irAEs.
 
To assess time to recovery from irAE (time to reduction of irAE by at least one grade), time to all irAEs reduced to \leq1, and time to resume ICI treatment: The date of starting treatment (i.e., Day 1) will be used for all time events in the study. Kaplan-Meier plots and confidence intervals will be used to summarize outcomes. Medians and associated 95% confidence intervals will be calculated, and comparisons between groups will be performed by log-rank tests. Cox proportional hazard models will be used to explore association between covariates and outcomes.
 
To assess recovery rate of irAE by CD24Fc (reduction of irAE by one grade) at D42 and response rate of ICI: The fractions will be reported along with 95% two-sided confidence intervals. Comparisons between arms will be performed by Fisher's Exact tests. We will also characterize the proportion who remain that either respond or have stable disease, compared to those who progress.
 
To assess PFS and OS: Kaplan-Meier plots and confidence intervals will be used to summarize PFS, and OS; 1-year OS rate will be reported; medians and associated 95% confidence intervals will be calculated, and comparisons between groups will be performed by log-rank tests. Cox PH models will be used to explore association between outcomes and covariates.
 
As exploratory analysis, we will summarize descriptively the relationship of response rates to tumor type (lung, GI, melanoma, breast, prostate) and to cellular immune response and explore the relationship using logistic regression.

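### Section 4.1's DLT list has no item for an isolated Grade 4 non-hematologic laboratory value, though it counts the same abnormality at Grade 3 when treatment is needed

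*Combined protocol and SAP*

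**What the plan says.** Section 4.1 lists eight DLT criteria. Item 1 is "Grade 4 non-hematologic toxicity (not laboratory"), and item 5, for Grade 3 clinical events, carries the same exclusion. Items 2 to 4 are hematologic. Item 6 opens "Any Grade 3 non-hematologic laboratory value if" and then gives four alternatives: clinical symptoms or signs, need for treatment, hospitalization, or persistence beyond one week. Item 7 is "AST and/or ALT elevation >20 x ULN with concurrent total bilirubin elevation to >5 x ULN", without initial evidence of cholestasis. Item 8 is death.

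An attribution limit follows: the event should be a "CD24Fc treatment emergent AE that is not associated to irAEs defined in enrollment". Two rules then use the count. The first dose is lowered "If DLT occurred in 2 patients during the first dose of CD24Fc dosing in the 14-day period", and later "The study will be terminated if >2 patients have DLT at this reduced dosing".

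Section 10.2 has its own definition: "dose limiting toxicity is defined as any new AE of" grade 3 or above that falls outside the irAE spectrum. The synopsis repeats it ("In phase I lead-in study, dose limiting toxicity is defined as any new AE of" that grade). No section says which definition feeds the rules in 4.1.

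**The concern.** A DLT list should not drop an event as it becomes more severe. The other parts of this list respect that. Hematologic events count at Grade 4 whatever their duration and at Grade 3 under conditions. Clinical non-hematologic events count at Grade 4 outright and at Grade 3 with exceptions. Only the laboratory part has no Grade 4 level. Item 4 adds a plus sign to the grade where higher grades are meant, and item 6 does not.

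At stake is a small count with a low threshold. Phase I has six patients and the dose is reduced at two DLTs, so the classification of one patient can decide whether the dose changes. With two definitions in the protocol, two careful readers could reach different dose decisions from the same six patients.

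**Working it through.** No figure in the plan is in dispute, so the check is one of classification. The test case is a patient enrolled for rash who develops new hypokalemia within 14 days of the first dose. An electrolyte is used because hepatic and renal values are listed as irAEs in Section 5.0 (items 4c and 4d) and might fall outside the 10.2 definition for that reason. In the isolated Grade 4 case there is no separate clinical toxicity and no sampled Grade 3 value that meets an item 6 condition.

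| 4.1 item | Scope | Isolated Grade 4 | Grade 3 needing replacement |
|---|---|---|---|
| 1 | Grade 4 clinical, laboratory excluded | no | no |
| 2 | Grade 4 hematologic | no | no |
| 3 | Neutrophils | no | no |
| 4 | Platelets | no | no |
| 5 | Grade 3 clinical, laboratory excluded | no | no |
| 6 | Grade 3 laboratory plus a condition | no (wrong grade) | **yes** |
| 7 | AST/ALT and bilirubin together | no | no |
| 8 | Death | no | no |
| 10.2 and synopsis | New AE, grade 3 or above, outside irAE spectrum | **yes** | **yes** |

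Effect on the two rules:

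- Dose reduction. Suppose one other patient has a listed DLT. With the Grade 4 patient, the 4.1 count is 1 + 0 = 1 and the dose stays. The 10.2 count is 1 + 1 = 2 and the dose is reduced. Had the same patient's value been Grade 3 and needed replacement, both counts would be 2.
- Termination. Suppose two patients at the reduced dose have listed DLTs. Adding the Grade 4 patient gives 2 under 4.1, which is not more than 2, and 3 under 10.2, which is.

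The following is pure illustration. The documents give no rate for isolated Grade 4 laboratory events, so both the DLT rate p and the share s of DLT patients with only the uncounted event are assumed. The chance of triggering dose reduction in six patients is P(X ≥ 2) = 1 − (1 − p)^6 − 6p(1 − p)^5, with p replaced by p(1 − s) when events go uncounted.

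- p = 0.10, s = 0: 1 − 0.5314 − 0.3543 = 0.114. With s = 0.10 the rate is 0.09 and the result is 0.095.
- p = 0.20, s = 0: 1 − 0.2621 − 0.3932 = 0.345. With s = 0.10 the rate is 0.18 and the result is 0.296.
- Expected uncounted patients per cohort, 6ps: 6 × 0.10 × 0.10 = 0.06 and 6 × 0.20 × 0.10 = 0.12.

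These figures show the direction of the effect. They do not estimate its size.

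**The case against.** The strongest reply is that few Grade 4 values would really escape. A value that recovers usually passes through the Grade 3 range, and item 6 does not restrict itself to the worst grade reached. A Grade 3 reading during treatment would therefore qualify. An event with clinical consequences can also be reported as a clinical toxicity under item 1, and Section 11.0.0 describes Grade 4 in just those terms. This stands, and it narrows the gap to values with no separate clinical toxicity and no sampled qualifying Grade 3 value. It does not close it. Table 1 schedules chemistry at the dosing visits, so an intermediate reading depends largely on unscheduled draws.

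A second reply is that the intent is plain. Section 4.0 acts on related toxicity of grade 3 or greater and points to 4.1. The Phase I primary endpoint and the Phase II toxicity monitoring in 10.4 use the same threshold. Nothing suggests that Grade 4 laboratory events should count for less. That makes a drafting slip the likely explanation, but the rule as printed still omits them.

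A third reply is that other safeguards would catch the event: removal from treatment (4.0, 6.7), the summary after the sixth patient (6.6) and monthly DSMC review (13.0). That is right for the patient and for oversight. None of them adds to the count in 4.1.

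A reader might also infer that such an event has already been seen with CD24Fc, from the possibly drug-related hyperglycemia in the 480 mg Phase IIa cohort. The documents do not support this. Sections 1.4.1 and 2.0.1 report it only in pooled grades, so Grade 4 is not established, and a Grade 3 value treated with insulin would meet item 6. The Phase IIa safety account in Section 2 also reports no laboratory abnormality that was an SAE or led to discontinuation. Seriousness and grade are different things, so that is not proof, but it points away from the inference.

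**Conclusion.** Item 6 is wrong as written, and the error is minor in reach. On a literal reading an isolated Grade 4 non-hematologic laboratory value is outside the 4.1 list, while its Grade 3 form is inside when an item 6 condition is met. The broader definition in 10.2 and the synopsis would count it, and the precedence of the two is not stated. The consequence is confined to the Phase I 14-day DLT count and the dose-reduction and termination rules that use it. The Phase I primary endpoint is unaffected.

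The conclusion assumes a literal reading of item 6, an event not attributed to the enrolling irAE, no separate clinical toxicity and no sampled qualifying Grade 3 value. Two stronger readings should be avoided. One is that all Grade 4 laboratory events are lost, or would pass unnoticed: the item 1, item 6 and item 7 routes and the other safeguards rule that out. The other is that the trigger probability falls by a known amount: any such figure rests wholly on assumed rates.

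**What to change.** Amend item 6 so that it applies to non-hematologic laboratory values of Grade 3 or higher, with its four conditions unchanged. Keep item 7: it counts without any of those conditions, so it still adds something. If the sponsor wants isolated transaminase rises left out, write that into item 6 as an explicit exception. Add one sentence stating that the amended 4.1 list governs the dose-reduction and termination rules in 4.1, and have 10.2 and the synopsis refer to it.

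The cost is a one-line amendment and one sentence, with no extra tests or patients. The downside is a possibly slightly higher DLT count, and so a slightly greater chance of dose reduction.
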